5.5.1.3. Multicenter Studies

The following investigative site pooling method will be used:

All investigative sites with fewer than 2 randomized patients per each treatment group with non-missing cluster headache attacks during baseline interval and at least 1 postbaseline value will be pooled together within each country and considered a single site for analyses. If this results in a pooled site still having fewer than 2 randomized patients per each treatment group, the pooled site will also be pooled with the next smallest site in that country, determined to be the site with the smallest number of randomized patients, or if more than 1 site meets that criterion, the smallest site with the lowest investigator number. If this results in a pooled site still having

fewer than 2 patients randomized to each treatment arm, these sites will be pooled together with the next smallest site in the geographic region. Two geographic regions are defined, including US and Canada combined, as well as Europe. If this still results in a site having fewer than 2 patients randomized to each treatment, then these sites will be pooled together with the next smallest site in the whole study.

All analyses will use pooled investigative sites. The actual investigative site numbers will be included in the listings.

5.5.1.4. Multiple Comparisons/Multiplicity

The primary efficacy analysis will be the overall treatment effect of GMB300 mg every 30 days versus placebo over Weeks 1 to 3 using a MMRM analysis, which is equivalent to the average of the MMRM-estimated weekly treatment effect over the 3-week period for change in weekly cluster headache attack frequency from baseline. The Type I error rate will be controlled at a 1-sided 0.025 level for the primary efficacy analysis.

A fixed sequential gatekeeper method will be utilized for testing secondary hypotheses to be eligible for inclusion in the proposed label. Specific details of the testing of the secondary gatekeeper objectives are provided in Section [5.5.8.2](#).

5.5.1.5. Analysis Populations

Three analysis populations, including the ITT population, the safety population, and the posttreatment population, are defined in Section [5.5.1](#).

5.5.1.6. Baseline and Postbaseline Definition

Table [CGAL.5.2](#) describes the rules for determining the patient population and baseline and postbaseline observations for each study phase and type of analysis. When “last of Visit x-x” is used in the table, the last nonmissing observation obtained in the visit interval will be used.

Table CGAL.5.2. Patient Population with Baseline and Postbaseline Definitions by Study Phase and Type of Analysis

Study Phase/Analysis	Patient Population	Baseline Observation	Postbaseline Observation(s)
Study Phase III			
Continuous secondary efficacy analyses (Repeated measures)	Patients in ITT population with a baseline and at least 1 postbaseline observation	Visit 3	All Visits 4-7
TEAEs	Safety population	All Visits 1-3 before dosing	Visit 3 after dosing through Visit 7
SAEs, Discontinuations due to AEs	Safety population	NA	Visit 3 after dosing through Visit 7
C-SSRS categorical analyses	Patients in safety population with a baseline and at least one postbaseline C-SSRS assessment	Recent history: All Visits 1-3 excluding lifetime ^a All prior history: Visits 1- 3 including lifetime ^a	All Visits 3.01-7
TE abnormal laboratory values	Patients in safety population with normal laboratory values at all nonmissing baseline visits (with respect to direction being analyzed) and who have at least 1 postbaseline observation	All Visits 1-3	All Visits 3.01-7
TE immunogenicity	Patients in safety population who are evaluable for TE ADA	Visit 3	All Visits 3.01-7
TE changes in vital signs and weight, ECG parameters	Patients in safety population with a baseline and at least 1 postbaseline observation	Last nonmissing value from Visits 1-3 for BP, pulse, and ECG All Visits 1-3 for weight and temperature	Visits 3.01-7

Patient Population with Baseline and Postbaseline Definitions by Study Phase and Type of Analysis

Study Phase/Analysis	Patient Population	Baseline Observation	Postbaseline Observation(s)
Continuous safety analysis of vital signs, weight, laboratory, and ECG parameters (Box-whisker plot)	Safety population	Last non-missing value from Visits 1-3	Visits 4-7
Study Phase III and IV Combined			
TE immunogenicity	Patients in safety population who are evaluable for TE ADA	Visit 3	All Visits 3.01-9
Study Phase IV			
Post TEAEs	Posttreatment population	All Visits 1-7	All Visits 7.01-9
SAEs, Discontinuations due to AEs	Posttreatment population	NA	All Visits 7.01-9
C-SSRS categorical analyses	Patients in posttreatment population with a baseline and at least 1 postbaseline C-SSRS assessment	Recent history: All Visits 1-7 excluding lifetime ^a All prior history: Visits 1-7 including lifetime ^a	All Visits 7.01-9
Post TE abnormal laboratory values	Patients in posttreatment population with normal laboratory values at all nonmissing baseline visits (with respect to direction being analyzed) and who have at least 1 postbaseline observation	All Visits 1-7	All Visits 7.01-9

Patient Population with Baseline and Postbaseline Definitions by Study Phase and Type of Analysis

Study Phase/Analysis	Patient Population	Baseline Observation	Postbaseline Observation(s)
Post TE changes in vital signs and weight, ECG parameters	Patients in posttreatment population and with a baseline and at least 1 postbaseline observation	Last nonmissing value from Visits 1-7 for BP, pulse and ECG All Visits 1-7 for weight and temperature	7.01-9

Abbreviations: ADA = anti-drug antibody; AE = adverse event; BP = blood pressure; C-SSRS = Columbia Suicide Severity Rating Scale; ECG = electrocardiogram; ITT = intent-to-treat; NA = not applicable; SAE = serious adverse event; TE = treatment emergent; TEAE = treatment-emergent adverse event.

Note: Visit 3.01 indicates the first unscheduled visit occurring after Visit 3 and prior to Visit 4.

a Lifetime is captured in the C-SSRS Visit 1 case report form.

5.5.2. Patient Disposition

The number and percentage of ITT patients who complete the study or discontinue early will be tabulated for all treatment groups for SP III and SP IV both overall and by visit. Reasons for discontinuation will be compared between treatment groups using Fisher's exact test for SP III with the ITT population. Descriptive statistics only will be presented for the treatment groups in SP IV. For patients who were randomized without drug injection, reasons for early discontinuation will be provided in a listing.

Patient allocation by investigator will be summarized for SP III for all ITT patients.

Patient allocation by investigator will also be listed for all SPs.

5.5.3. Important Protocol Deviations

Important protocol deviations that potentially compromise the data integrity and patients' safety will be summarized by treatment for the ITT population.

Section 7 (appendix) lists the categories, subcategories, study-specific terms of important protocol deviations, and source of identification. Per study team's discretion, for non-programmable protocol deviation, additional categories and subcategories other than the ones on Section 7 can always be added into the final nonprogrammable protocol deviations list as deemed necessary.

Tables and listings of subjects with important protocol deviations will be provided for the ITT population.

5.5.4. Patient Characteristics

The following patient characteristics at baseline will be summarized by treatment group for all ITT patients:

- demographic (age, gender, race, ethnicity, country, region, height, weight, body mass index)
- baseline disease characteristics:
- number of weekly cluster headache attacks
- average severity of cluster headache pain for the cluster headache attack days
- weekly total cluster headache attack duration
- weekly number of times using oxygen
- weekly number of times using oral triptan, sumatriptan nasal spray, or zolmitriptan nasal spray
- weekly number of times using sumatriptan Sc
- weekly number of times using acetaminophen/paracetamol or NSAIDs
- number of times using oxygen per cluster headache attack

- number of times using oral triptan, sumatriptan nasal spray, or zolmitriptan nasal spray per cluster headache attack
- number of times of using sumatriptan Sc per cluster headache attack
- number of times using acetaminophen/paracetamol or NSAIDs per cluster headache attack
- total weekly dose for oral triptan, sumatriptan nasal spray, and zolmitriptan nasal spray combined
- total weekly dose for sumatriptan Sc
- total weekly dose for oral triptan
- total weekly dose for sumatriptan nasal spray
- total weekly dose for zolmitriptan nasal spray
- prior cluster headache history in last 7 days prior to Visit 1
- baseline alcohol, tobacco, caffeine, and nicotine consumption
- medical history and pre-existing conditions

Comparisons between treatment groups will be performed using Fisher's exact tests for categorical data and analysis of variance (ANOVA) with treatment and pooled investigative site as independent variables in the model for continuous data.

Medical history and pre-existing conditions will be summarized by descending frequency of preferred term (PT) within system organ class (SOC), and by descending frequency of PT respectively, and comparison between treatment groups will be performed using Fisher's exact test. Medical history is defined as illness(es) that ended prior to the signing of informed consent. Pre-existing conditions are medical events ongoing at the time of informed consent.

5.5.5. *Exposure to Investigational Product*

Patients will receive the investigational product (IP) at the following planned time points:

- Week 0 (Visit 3)
- Week 4 (Visit 5)

The following information will be recorded on the electronic case report form (eCRF) for each dose:

- confirmation that the patient received the IP
- date and time of administration

5.5.5.1. Duration of Exposure

From the information recorded on the eCRF, the following will be derived:

- Duration of exposure in days calculated as Treatment End Date (disposition date in SP III) – First date IP administered + 1
- Number and percentage of patients with 1 full dose or 2 full doses administered

Comparisons between treatments using safety population for duration of exposure will be performed using an ANOVA with treatment and pooled investigative site in the model.

The number of full doses will also be summarized.

5.5.5.2. Treatment Compliance

Treatment compliance will be calculated as follows

$$\text{(number of full doses received)/(Number of intended full doses)*100}$$

Note, full dose means that patients have to receive all 3 injections. For patients that are early discontinued, number of intended full doses will only include scheduled doses prior to discontinuation. Comparisons between treatments in the ITT population for treatment compliance will be performed using an ANOVA with treatment and pooled investigative site in the model.

5.5.6. *Electronic Patient-Reported Outcome Diary Compliance*

Electronic patient-reported outcome diary compliance at each weekly interval (including baseline, Weeks 1, 2, 3, 4, 5, 6, 7, and 8) will be calculated. Diary compliance at each interval is calculated as follows:

$$\frac{\text{Actual number of diary entry days in the interval * 100}}{\text{Expected number of diary entry days in the interval}}$$

The diary entry can only be saved and submitted after all the required ePRO questions are answered, so the actual number of diary entry days represents the total number of days with non-missing answer to all the required cluster headache attack ePRO questions.

The expected number of diary entry days is calculated as the (last calendar date - the first calendar date in each interval + 1).

Comparisons between diary compliance for each interval separately will be performed using an ANOVA with treatment and pooled investigative site in the model.

Compliance will also be listed by weekly interval for each patient.

5.5.7. *Concomitant Therapy*

The proportion of patients who received concomitant medication collected from eCRF will be summarized by PT separately for all ITT patients for both SP III and SP IV. Abortive medications for cluster headache attack collected through ePRO diary will be summarized separately by PT for all ITT patients for SP III. If there are different PTs for salt forms of an abortive medication, these PTs will be combined for the medication in the summary.

Concomitant therapies for SP III are those that stopped during SP III or continued in SP III. If medication started and stopped on the same day of first injection, it will still be considered as concomitant medication for SP III. If a medication started before the first day of injection but

stopped on the same day of injection, then it will not be counted as concomitant medication for SP III. Concomitant therapies for SP IV are those that either started, stopped, or continued in SP IV.

Treatment group comparisons will be done using Fisher's exact test for SP III with the ITT population. Descriptive statistics only will be presented for the treatment groups in SP IV with posttreatment population.

5.5.8. Efficacy Analyses

5.5.8.1. Primary Outcome and Methodology

The primary analysis will be conducted by a REML-based, MMRM analysis using all the longitudinal observations from Weeks 1 to 3. The analysis of the primary outcome will be the main effect of treatment between GMB 300 mg and placebo across Weeks 1 to 3 of the treatment phase from a repeated measures analysis on mean change from baseline in the weekly attack frequency. This provides the average treatment effect over the 3-week period. Baseline is defined as the last 7 days in the eligibility report (prerandomization diary phase). In addition to the primary endpoint results, the mean profiles for GMB300mg and placebo over the 3-week period will also be reported from the MMRM.

The MMRM model for the primary analysis only uses the first 3 weeks of double-blind treatment phase data to avoid impact of the data from later weeks when patients may start to get into the remission period.

The model for the primary analysis will include the fixed, categorical effects of treatment, gender, pooled investigative site, week, and treatment-by-week interaction, as well as the continuous, fixed covariates of baseline value. An unstructured covariance structure will be used to model the within-patient errors. The Kenward-Roger (Kenward and Roger 1997) approximation will be used to estimate denominator degrees of freedom. If the model does not converge with both the Hessian and the G matrix being positive definite under the default fitting algorithm used by PROC MIXED, the Fishers' scoring algorithm will be implemented by specifying the SCORING option in SAS®. If the model still fails to converge, the model will be fit using covariance matrices of the following order specified by a decreasing number of covariance parameters until convergence is met:

- heterogeneous Toeplitz
- heterogeneous first-order autoregressive
- Toeplitz
- first-order autoregressive

If necessary, both the default and the scoring fitting algorithms will be used in the prespecified order before proceeding to the next covariance structure in the sequence. For models where the unstructured covariance matrix is not utilized, the sandwich estimator (Diggle et al. 1994) will be used to estimate the standard errors of the fixed effects parameters. The sandwich estimator is

implemented by specifying the EMPIRICAL option in SAS®. When the sandwich estimator is utilized, the Kenward-Roger approximation for denominator degrees of freedom cannot be used. Instead, the denominator degrees of freedom will be partitioned into between-subject and within-subject portions by the DDFM=BETWITHIN option in SAS®. SAS® PROC MIXED will be used to perform the analysis.

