Clinical Protocol Synopsis: Study I5Q-MC-CGAL

Name of Investigational Product: LY2951742 (a humanized monoclonal antibody that binds to and neutralizes CGRP)	
Title of Study: A Phase 3 Randomized, Double-Blind, Placebo-Controlled Study of LY2951742 in Patients with Episodic Cluster Headache	
Number of Planned Patients: Entered: 231 Enrolled/Randomized: Planned 162 Completed: 146	Phase of Development: 3
Length of Study: approximately 18 months Estimated first patient visit: Apr 2015 Estimated last patient visit: Sep 2016	
Primary Objective: The primary objective of this study is to assess the efficacy of LY2951742 300 mg every 30 days compared with placebo in reducing the frequency of weekly cluster headache attacks in patients with episodic cluster headache. The primary outcome measure will be the weekly cluster headache attack frequency. The primary endpoint will be the overall mean change from baseline in weekly cluster headache attack frequency across Weeks 1 to 3 with LY2951742 compared with placebo. Baseline is defined as the last 7 days in the eligibility report (pre-randomization diary phase).	
Gated Objective: To assess the efficacy of LY2951742 compared with placebo in the proportion of patients meeting response at Week 3. For this analysis, response is defined as a reduction from baseline of 50% or greater in the weekly cluster headache attack frequency.	

Other Secondary Objectives:

- To assess whether LY2951742 is superior to placebo on the following:
 - a. The proportion of patients with a 50% or greater reduction in the weekly number of cluster headache attacks from baseline for each weekly interval through Week 8
 - b. The proportion of patients with a 30% or greater reduction in the weekly number of cluster headache attacks from baseline for each weekly interval through Week 8
 - c. Mean change in the weekly cluster headache attack frequency from baseline for each weekly interval through Week 8
 - d. Proportion of patients reporting a score of 1 (“very much better”) or 2 (“much better”) on the Patient Global Impression of Improvement (PGI-I) at Week 4 and Week 8.
- To compare the safety and tolerability of LY2951742 with placebo in patients with episodic cluster headache using the following measures:
 - a. spontaneously reported treatment-emergent adverse events (TEAEs)
 - b. serious adverse events (SAEs)
 - c. discontinuation rates

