- Addition of analysis for change from baseline in total weekly dose of sumatriptan Sc, sumatriptan nasal spray, and zolmitriptan nasal spray separately as well as combined.

Statistical Analysis Plan Version 3 was approved prior to IA1. The changes incorporated in Version 3 are as follows:

- Posttreatment follow-up phase safety analyses will have only 1 baseline.
- A section on protocol violations to be identified was added.
- Sensitivity analyses were updated, to be consistent with other Phase 3 studies of LY2951742.
- Infections section will only deal with upper respiratory tract infections; analyses were modified to be consistent with other Phase 3 studies of LY2951742.
- For Columbia-Suicide Severity Rating Scale (C-SSRS), 1 bullet was split into 2 to enhance readability, and baseline definition for improvement from baseline analysis was clarified.

- Criteria for sustained elevation in diastolic blood pressure was changed to be consistent with the single time point analysis.
- An additional criteria threshold for QTc increase was added.
- Analyses of elevations in hepatic laboratory tests were clarified, and an additional subset was added.
- Immunogenicity analyses were updated to be consistent with other Phase 3 studies of LY2951742.
- An additional subgroup analysis category, for age, was added.
- Some minor corrections and clarifications were made.

Statistical Analysis Plan Version 4 was approved after the last patient was randomized and prior to interim analysis (the first and final assessment of primary efficacy endpoint after all patients completed double-blind phase, which is the first unblinding to study team). Enrollment in the trial was terminated (due to enrollment infeasibility) prior to reaching the sample size target for the originally planned interim analysis. Therefore, the planned interim analysis for sample size re-estimation did not occur.

In the SAP Version 4, the updates were made mainly for incorporating the recent learnings from migraine data or for consistency across the galcanezumab program. The changes incorporated in Version 4 of the SAP are summarized as follows:

- LY2951742 was replaced by galcanezumab in the body of the SAP.
- Consistent with the primary endpoint and analysis methodology for the pivotal migraine studies, the primary endpoint was updated to be the overall treatment effect over the Weeks 1 to 3 during the double-blind treatment phase, rather than the treatment effect at the single time point, Week 3.

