5.2. Determination of Sample Size

The study is planned to have a minimum of approximately 162 patients randomized 1:1 to placebo or galcanezumab 300 mg with the opportunity to increase the final sample size at an interim analysis if indicated in order to maintain a well-powered study. To preserve blinding, details of the sample size and power calculations are omitted from this SAP and are provided in a separate document to the Ethical Review Board (ERB).

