Treatment effects will be evaluated based on a 2-sided significance level of 0.05 for all the other efficacy and safety analyses. The 95% confidence intervals for the difference in least-square means (LSMeans) between treatment groups will be presented. Adjustments for multiple comparisons for the analyses corresponding to the primary and gated secondary objectives are described in the sections on the primary and secondary efficacy analyses below. There will be no adjustments for multiplicity for analyses of other data.

A repeated measures analysis refers to a restricted maximum likelihood (REML)-based, mixed-effects repeated measures (MMRM) analysis using all the longitudinal observations at each postbaseline visit/week.

Categorical comparisons between treatment groups for safety measures will be performed using Fisher's exact tests, where appropriate.

Any change to the data analysis methods described in the protocol will require an amendment ONLY if it changes a principal feature of the protocol. Any other change to the data analysis methods described in the protocol, and the justification for making the changes, will be described in the SAP and/or in the clinical study report (CSR).

Additional exploratory analyses of the data will be conducted as deemed appropriate.

Statistical analysis of this study will be the responsibility of Eli Lilly and Company (Lilly) or designee. SAS® software will be used to perform most or all statistical analyses.

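### If the unstructured model fails, the primary MMRM falls back to an uncorrected sandwich standard error, and two-sided type I error on that path is about 5.5-9.5% instead of 5%

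*SAP*

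**What the plan says.** SAP 5.5.8.1 fits the change in weekly attack frequency over Weeks 1 to 3. The fixed effects are treatment, gender, pooled site, week and treatment-by-week, with baseline as a covariate. An unstructured covariance with Kenward-Roger comes first. If it fails under both the default and the scoring algorithm, four simpler structures follow in order: heterogeneous Toeplitz, heterogeneous AR(1), Toeplitz and AR(1). The rule for all four begins "For models where the unstructured covariance matrix is not utilized, the sandwich estimator", which is "implemented by specifying the EMPIRICAL option in SAS". Kenward-Roger is then replaced by DDFM=BETWITHIN. Protocol 12.2.7.1 has the same rule.

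SAP 5.5.1.3 sets the site effects. "All investigative sites with fewer than 2 randomized patients per each treatment group" are pooled within country, then region, then the whole study, until each pooled site reaches that minimum.

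On error control, SAP 5.5.1.4 says "The Type I error rate will be controlled at a 1-sided 0.025 level for the primary efficacy analysis". Table CGAL.5.3 sends the continuous secondary and exploratory diary measures, over eight weeks, to the same kind of model.

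**The concern.** The classical sandwich estimates variance from raw residuals. Fitting a parameter for each site shrinks those residuals, so the variance is too small unless between-patient parameters are few relative to patients. Between-within degrees of freedom change the t reference but not the variance. The plan thus gives up its small-sample protection at the step where it adopts a downward-biased standard error.

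At stake is the stated alpha of the confirmatory test on this path. That test also opens the gate to the 50% response endpoint (SAP 5.5.8.2). Elsewhere the SAP allows for sparse sites: 5.5.1.1 leaves site out of the responder models to help convergence, and 5.5.11 lets it be dropped from the negative binomial model. The primary fallback has no such provision.

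**Working it through.** **Inputs from the documents**
- Alpha: one-sided 0.025 (SAP 5.5.1.4). This agrees with SAP 5.5.1, "Treatment effects will be evaluated based on a 2-sided significance level of 0.05", since 2 × 0.025 = 0.05.
- Planned size: 162 randomised 1:1 (SAP 5.2), with 146 planned completers (Protocol synopsis), so 16/162 = 9.9% planned loss.
- Between-patient parameters with S pooled sites: intercept, treatment, gender, baseline and S-1 site terms, so p = S + 3.
- Ceiling on S: at least 2 patients per arm means at least 4 per pooled site, so S ≤ N/4. That is 40 at N=162, 30 at N=120, 25 at N=100 and 20 at N=80.

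**Assumptions**
- Final N is not given. SAP section 3 says "Enrollment in the trial was terminated (due to enrollment infeasibility) prior to reaching the sample size target" for the originally planned interim analysis. Range used: 80 to 162.
- The number of pooled sites is not given. Range used: 5 to N/4.

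**Reference.** The plan has no derived figure to reproduce, because its power inputs are kept in a separate document. The first-choice path was simulated under the null instead (unstructured, model-based standard error, t with N-p degrees of freedom standing in for Kenward-Roger). It gave 4.7-5.2% two-sided, so the benchmark is sound.

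**Approximation for the fallback**
- Ratio of sandwich SE to true SE: r = sqrt(1 - (S+3)/N)
- Two-sided type I error = 2 × P(t with N-p df > r × t_crit)

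Example, N=162 and S=20: p = 23; r = sqrt(1 - 23/162) = 0.926; df = 139; t_crit = 1.977; r × t_crit = 1.831; type I error = 6.9%.

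**Simulation.** 8,000 null trials per row, three weeks, complete data, heterogeneous Toeplitz working covariance, uncorrected sandwich, between-within df. Treatment was balanced within site as a stand-in for minimization.

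| N | S | SE ratio r | Approx., two-sided | Simulated, two-sided | Simulated, one-sided (nominal 2.5%) |
|---|---|---|---|---|---|
| 162 | 8 | 0.965 | 5.8% | 5.9% | 2.8% |
| 162 | 10 | 0.959 | 6.0% | 6.1% | 2.9% |
| 162 | 20 | 0.926 | 6.9% | 7.1% | 3.6% |
| 162 | 30 | 0.892 | 8.0% | 7.9% | 4.0% |
| 162 | 40 | 0.857 | 9.2% | 9.1% | 4.7% |
| 120 | 10 | 0.944 | 6.4% | 6.3% | 3.0% |
| 120 | 20 | 0.899 | 7.8% | 7.7% | 3.9% |
| 120 | 30 | 0.851 | 9.4% | 9.4% | 4.9% |
| 100 | 8 | 0.943 | 6.4% | 6.1% | 2.8% |
| 100 | 15 | 0.906 | 7.5% | 7.3% | 3.9% |
| 100 | 25 | 0.849 | 9.5% | 9.5% | 4.6% |
| 80 | 20 | 0.844 | 9.6% | 9.0% | 4.6% |

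The low end of the range is S=5 at N=162: r = sqrt(1 - 8/162) = 0.975, giving 5.6% by the approximation. Separate simulations agree: 5.4% (N=162, S=10), 6.6-6.7% (N=162, S=20), 8.0-8.4% (N=100, S=20) and 8.8-8.9% (N=80, S=16). Skewed data at N=162, S=20 gave 6.6%.

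**Cause and repair.** Scaling the variance by N/(N-(S+3)) brings the table's scenarios back to 4.6-5.2%. A leverage-corrected sandwich gave 4.5-5.3%.

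**How likely is the fallback?** The 3-week unstructured matrix has 3 × 4/2 = 6 parameters, and heterogeneous Toeplitz has 3 + 2 = 5. The unstructured estimate was positive definite in all 13 × 8,000 = 104,000 simulated trials. Those used complete data and a purpose-written REML routine, so they do not test PROC MIXED itself. The 8-week matrix has 8 × 9/2 = 36 parameters. Eight-week checks of the uncorrected sandwich gave 7.3% (N=100, S=15) and 8.5% (N=100, S=20).

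**Would model-based errors do instead?** In an 8-week simulation with a misspecified AR(1) fallback, the model-based test rejected about 10.9%, the plan's sandwich 7.7% and the corrected sandwich 4.7%. A large-sample check with true exchangeable correlation 0.7 and AR(1) working covariance agrees. The model-based SE is about 19% too small over eight weeks, and 2 × P(Z > 0.81 × 1.96) is about 11%. Over three weeks it is about 3% too small, giving 5.7%.

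**The case against.** The strongest reply is that this path will probably never be taken for the primary endpoint. A 6-parameter matrix rarely fails under two algorithms, so the unconditional type I error of the primary test stays close to nominal. That stands, and a reader who inferred that the primary analysis as a whole runs above 5% would be wrong.

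Second, SAP 5.5.11 already plans a permutation test of the primary MMRM statistic, with the exact minimization and site-pooling algorithms and 100,000 permutations. It recalibrates the statistic whatever the bias in its standard error. This stands in part. The test would expose the inflation, but no rule lets it override the primary p-value.

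Third, the size depends on an unstated site count. Two patients per arm is a floor, not a typical size, and the pooling rule limits the count. A reader might infer many site effects and an error of 7-10%. The documents do not support that. By the approximation, 7% needs about 21 pooled sites at N=162 or 12 at N=100, and the pooling ceiling keeps the maximum near 9.5%. Short simulations can print more than 10%, but with 1,500 trials the Monte Carlo standard error is sqrt(0.09 × 0.91/1,500) = 0.7 points.

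Fourth, the sandwich is there for a reason: it protects against a wrong fallback covariance. That stands, and it limits the choice of remedy.

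Fifth, the 8-week analyses lie outside the gate and carry no multiplicity adjustment (SAP 5.5.1). For them the issue is standard errors that are too small and intervals that are too narrow, not loss of the trial's controlled alpha.

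**Conclusion.** The gap is real but conditional. If the fallback is used, the prespecified standard error is about 2.5-16% too small and the two-sided type I error is about 5.5-9.5%, so the alpha claimed in SAP 5.5.1.4 does not hold on that path. At the planned N with 10 or fewer pooled sites the error is about 6% or less. With 4-5 patients per site at N=80-100 it is about 8-9.5%.

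These figures assume N between 80 and 162, S between 5 and N/4, complete weekly data and treatment balanced within site. The trigger probability cannot be derived from the documents. It appears low for the 3-week model, while the 8-week models offer more room for failure. The point is worth correcting because the repair is cheap and the path is a written part of the confirmatory analysis.

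**What to change.** In SAP 5.5.8.1 and Protocol 12.2.7.1, replace the classical sandwich in the fallback with a small-sample leverage-corrected one. One implementation is PROC GLIMMIX with EMPIRICAL=ROOT, normal distribution, identity link, the same mean model and between-within degrees of freedom. Apply the same rule to the continuous secondary MMRMs.

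Alternatively, for the primary endpoint only, state that the permutation p-value already planned in SAP 5.5.11 is decisive at one-sided 0.025 if the fallback is used, with every permuted data set analysed under the same fallback structure. This repairs the test but not the confidence interval, so the corrected sandwich is the more complete option.

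Do not drop the sandwich for model-based Kenward-Roger standard errors: they do not protect against a misspecified fallback covariance, and in the 8-week check they did worse than the present rule.

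The cost is a sentence in each document and a program change, made before unblinding. Intervals become slightly wider, and only if the fallback is used.
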